The FAT_{MAX} test is an incremental-graded cycling test to volitional exhaustion originally designed upon a previously described and validated protocol (GE_{35/5}) in endurance trained cyclists [74]. The FAT_{MAX} protocol that will be utilised in the current study has also been validated in individuals with low cardiorespiratory fitness levels ($\geq 40 \text{ mL} \cdot \text{min}^{-1} \cdot \text{kg}^{-1} \dot{V}\text{O}_{2\text{peak}}$) [75] and will likely last between 20 – 35 minutes. The FAT_{MAX} tests were adapted in an attempt to more confidently determine peak fat use and the intensity at which this occurs (FAT_{MAX}) in individuals with a wide range of cardiorespiratory fitness levels. All tests will be completed on a mechanically-braked cycle ergometer (Monark Peak Bike Ergomedic 894E, Varberg, Sweden). Figures 3 and 4 depict the two similar FAT_{MAX} protocols that will be used.

The duration of the first seven stages are 4-minutes with approximate 25-watt increments (except for the 10-watt first stage increment in protocol 1; see Figures 3 and 4 for exact watt increments). From stage 8 onwards, stage duration was shortened to 2-minutes together with

greater watt increments between stages (approximate 50-watt increases) until volitional exhaustion was reached. The aim of this adjustment was to twofold; 1) To increase the sensitivity of the protocol to measure / capture peak fat use in the beginning stages and 2) To ensure volitional exhaustion and peak oxygen consumption ($\dot{V}O_{2peak}$) were quickly attained to reduce the confounding of fatigue. The revolutions per minute (RPM) are 30, 40 and 60 RPM for the first, second and third stage in FAT_{MAX} Protocol 1, and 40 and 60 RPM for the first and second stage in FAT_{MAX} Protocol 2, where a cadence of 80 RPM is then maintained for the remainder of the stages.

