To keep the FAT_{MAX} protocols simple and easy to perform for the participant, RPM was standardised to multiples of 10 and kept constant where possible. This led to slight discrepancies between the intended and actual watts at each stage (see figures 3 and 4). With 0.1kg representing the lowest weight available at the University of Bath facilities, the required applied mass to achieve the desired watts at each stage was not possible when holding RPM constant. Additionally, the weight cage on the Monark Ergonomic 894E peak bike applies a constant mass of 1kg, thus to elicit approximately 30, 40 and 65 watts, the RPM at these stages were lowered. The two protocols were developed upon a validation study of the FAT_{MAX} Protocol 2 [75]. In this study participants who had low cardiorespiratory fitness levels often reached peak fat use in the first stage (40-watts). Thus, a FAT_{MAX} protocol with a first stage of 30-watts was designed in an attempt to more confidently measure peak fat use in individuals with a wide range of cardiorespiratory fitness levels. The FAT_{MAX} test protocol to be completed by the participant will be decided at Visit 1 after their exercise habits have been verbally and written assessed via the health screening and demographic / lifestyle questionnaires. Individuals who self-report in engaging in little or no exercise per week / are physically inactive will complete FAT_{MAX} Protocol 1, whereas regular exercisers will complete FAT_{MAX} Protocol 2. Each individual participant will complete the same FAT_{MAX} Test Protocol on the Main Trial days (Visit 2 and 3) to ensure comparability.

To commence the FAT_{MAX} Test, participants will be set-up on the cycle ergometer through adjustment of saddle and handlebar height and distance to their preferred position. This will then be checked and recorded by the researcher to ensure correct and ensure standardisation for both tests. Participants will then be explained the respective protocol (See figures 3 and 4) and offered the opportunity to ask any questions. A mouthpiece will then be handed to participants for 2-minutes in the position expired gas samples will be collected to accustom

them to breathing through the mouthpiece to reduce the likelihood of hyperventilation and try to ensure data accuracy.

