	Fasting measures of Adipokines: Leptin, Adiponectin
	Fasting measures of Catecholamines: epinephrine and norepinephrine
	Fasting measures of sex hormones: 17 beta-estradiol, testosterone, progesterone
	Fasting pancreatic derived hormone concentrations: insulin and glucagon
	Hydration Status: Urine Specific Gravity
	Age (years)
	Sex
	Ethnicity
	Smoking Status
	Medication / Supplement Use
	Dietary Patterns / Requirements
	Body Fat Percentage
	Lean Body Mass (kg)
	Body Fat Distribution
	Waist and Hip Circumference
	Fat Mass Index
	Genotype analysis
	Skeletal Muscle Characteristics (Protein Content and / or Activity)
	Adipose Tissue Characteristics (Protein Content and / or Activity)

Data will be checked for normal distribution prior to analysis via Shapiro-Wilk's normality test and visual inspection of histograms. Parametric tests will be conducted on normally distributed data. Non-normally distributed data will be log-transformed if appropriate or the equivalent

non-parametric tests will be conducted. Statistical significance will be set at $P < 0.05$. The statistical analysis for the study objectives identified above are as follows:

- 1) The effect of body composition on whole-body fat use will be tested by separating groups into defined categories (e.g. lean, overweight or obese) and conducting a one-way ANOVA and mixed design model. The latter to test for any interaction effects across the two main trial days.
- 2) To identify determinants / characteristics that may be associated with whole-body fat use, correlation analysis will firstly be conducted between whole-body fat use at rest and during exercise with each variable. Statistically significant correlates will then be added to a follow-up hierarchical regression analysis to predict whole-body fat use at rest and during exercise.
- 3) At a group level, intra-individual variation in whole-body fat use will be tested by a paired sample t-test. A range of further reliability / variability tests will be conducted to comprehensively determine intra-individual variation: Pearson correlation coefficient, Intra Class Correlation, Coefficient of Variation, Bland-Altman plots with 95% Limits of Agreement and Typical Error. Additionally, individual data will be plotted on graphs alongside group means.

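### The low-fitness validation claimed for the FATmax test comes from a study of Protocol 2; Protocol 1, given to inactive participants, has none reported, and reliability is not split by protocol

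*Combined protocol and SAP*

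**What the plan says.** The section on the incremental cycling test (FATmax) states, in the singular, that the "protocol that will be utilised in the current study has also been validated in individuals with low cardiorespiratory fitness levels". It cites reference 75, which the reference list marks as in preparation. The same paragraph then says that "Figures 3 and 4 depict the two similar FAT_{MAX} protocols that will be used".

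Later in that section:

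- On what was studied: "The two protocols were developed upon a validation study of the FAT_{MAX} Protocol 2 [75".
- On what was found: "In this study participants who had low cardiorespiratory fitness levels often reached peak fat use in the first stage (40-watts".
- On the response, a "protocol with a first stage of 30-watts was designed in an attempt to more confidently measure peak fat use". This is Protocol 1.
- On allocation: "Individuals who self-report in engaging in little or no exercise per week / are physically inactive will complete FAT_{MAX} Protocol 1". Regular exercisers take Protocol 2, and each person repeats the same protocol at Visits 2 and 3.

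In Statistical / Data Analysis, item 3 begins: "At a group level, intra-individual variation in whole-body fat use will be tested by a paired sample t-test". It adds Pearson correlation, ICC, CV, Bland-Altman limits of agreement, typical error and plots of individual data. It names no strata. The subgroup examples under objective 4 do not include the FATmax protocol. Item 4 then assesses inter-individual variation after allowing for the within-person error.

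**The concern.** The primary outcome, the maximal rate of fat oxidation, is read from this test. The validation statement tells the reader that the test works in people of low fitness. The later text ties that evidence to Protocol 2, which inactive participants will not take. It also reports that low-fitness people often peaked at Protocol 2's lowest workload. A peak at the lowest workload is not bracketed from below, because no lower stage shows the rate falling away.

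Two separate things are at stake. The first is peak capture: whether the recorded maximum is the true maximum in participants on Protocol 1. The second is repeatability. Protocol is allocated by exercise habit, and the introduction names activity and fitness as influences on fat oxidation. Any difference in measurement error between the protocols would therefore line up with variables under study. Item 3 as written gives one set of reliability figures across both protocols.

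**Working it through.** **1. The statements side by side.** The claim concerns one protocol, low-fitness people and reference 75. The later text says that reference 75 studied Protocol 2, that low-fitness participants in it often peaked at stage 1, that Protocol 1 followed from this, and that Protocol 1 goes to the inactive. No section reports a validation of Protocol 1. How often the first-stage peaks occurred, and the criterion used for validation, are not given.

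**2. How far the protocols differ (Figures 3 and 4).** The tables imply watts = applied mass × RPM × k. From Protocol 1 stage 14, k = 518.153/(6.6 × 80) = 0.98135. Stage 1 of Protocol 1 is then 1 × 30 × 0.98135 = 29.44 W (printed 29.440), and stage 1 of Protocol 2 is 1 × 40 × 0.98135 = 39.254 W (printed 39.254). All 28 printed values reproduce to within 0.001 W except Protocol 2 stage 2 (64.779 printed, 64.769 computed), which is trivial.

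- The added first stage is 39.254 − 29.440 = 9.8 W lower.
- Protocol 1 stages 2 to 7 match Protocol 2 stages 1 to 6 in mass, cadence and 4-minute duration (nominally 40 to 165 W).
- Protocol 1 has no 4-minute stage at 190 W, and the loads differ again from stage 8 (211.972 v 243.375 W).

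**3. What pooling could mask (all inputs assumed).** Set Protocol 2's typical error to 1 and the between-person SD within each protocol to 2. Let r be Protocol 1's typical error (1.5 or 2), p the share on Protocol 1 (0.25, 0.50 or 0.75), and d the mean difference between the groups (0, 2 or 4).

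- Pooled within-person variance: W = p·r² + (1 − p).
- Pooled between-person variance: B = 4 + p(1 − p)d².
- Pooled ICC = B/(B + W). Within Protocol 1 it is 4/(4 + r²), which is 0.64 or 0.50. Within Protocol 2 it is 4/5 = 0.80.

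Worked case, p = 0.5, r = 2, d = 2: W = 2.5, so the pooled typical error is √2.5 = 1.58, which is 79% of Protocol 1's value of 2. B = 5, so the pooled ICC is 5/7.5 = 0.67, against 0.50 in Protocol 1.

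Over the whole grid, the pooled typical error is 66% to 93% of Protocol 1's and 1.15 to 1.80 times Protocol 2's. The pooled ICC is 0.55 to 0.84. It exceeds Protocol 1's own ICC by as little as 0.03 (p = 0.75, r = 1.5, d = 0) and as much as 0.30 (p = 0.25, r = 2, d = 4).

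**4. Consequence for item 4, in the same worked case.** Observed single-visit variance is 4 + 4 = 8 on Protocol 1 and 4 + 1 = 5 on Protocol 2. Subtracting the pooled 2.5 leaves 5.5 and 2.5, where the true value is 4 in both. The errors cancel over the whole sample, but not for individuals or for groups that differ in their mix of protocols.

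**5. Repeatability is not peak capture (all inputs assumed).** A simulation used a parabolic fat-oxidation curve with half-width 80 W, true peak intensity with mean 25, 35 or 45 W and SD 15 W, visit-to-visit SD 5 W, and measurement noise of 2% of the peak rate. The first stage held the recorded peak in 27% to 70% of Protocol 1 tests and 67% to 95% of Protocol 2 tests. At a mean of 25 W, Protocol 2 gave the same stage at both visits in 96% of people while recording a mean of 40.4 W against a true mean of 25.5 W. A truncated test can repeat very well and still be biased.

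**The case against.** The protocol reports the first-stage problem openly and adds a lower stage to deal with it. Protocol 1 is a small downward extension of the studied test, with most of its 4-minute stages in common. Reference 75 cannot be seen, and first-stage peaks in some participants do not refute validation on an unstated criterion. Item 3 does not forbid a split and plans individual plots. Typical error and limits of agreement rest on within-person differences, so a mean gap between the protocol groups does not inflate them. The study is exploratory.

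Most of this stands and limits the point. It does not correct the validation sentence, and it does not supply an error estimate for each protocol. Unequal error is averaged in the pooled typical error even with no mean gap.

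Three stronger readings are tempting, and the documents do not support them:

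- **That item 3 conceals a failed validation.** Item 3 measures test-retest variation. Neither a pooled nor a split version would show whether the peak was captured.
- **That Protocol 1 measures badly.** The documents report no validation of it. They do not report that it fails.
- **That the ≥ 40 fitness limit shows the wrong people were studied.** The sign sits oddly with the word low in the same sentence, but it may be a typing or text-conversion error.

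**Conclusion.** The concern holds in a limited form. The validation statement goes further than the rest of its own section supports: the evidence is for Protocol 2, and Protocol 1 is a later adaptation with no validation reported. Separately, item 3 as written gives one reliability estimate across two test sequences allocated by exercise habit, and provides no other error estimate for item 4. A difference in repeatability could therefore be masked.

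The size of any such difference is unknown. The figures above illustrate what could happen under assumed error ratios, splits and mean gaps; none of those inputs is in the documents. They range from negligible masking to a pooled ICC of 0.80 where Protocol 1's own is 0.50. Peak capture is a distinct question, and the documents plan no report that addresses it. The change is worth making because it serves objective 3 and is cheap; the point does not invalidate the study.

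**What to change.** 1. **Wording.** Reconcile the two parts of the FATmax section. Limit the validation statement to Protocol 2, describe Protocol 1 as a new adaptation whose validation is not yet reported, and check the ≥ 40 sign.
2. **Item 3, exercise outcomes.** Report typical error, CV, limits of agreement and ICC for each protocol with confidence intervals, alongside the pooled values. Resting outcomes need no split, since no cycling test precedes them on the day.
3. **Item 4, exercise outcomes.** Use the protocol-specific within-person error.
4. **Peak capture.** Report the number and proportion of tests whose highest fat oxidation falls at stage 1, by protocol.

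The cost is text and a stratified run of planned analyses on data already to be collected. The downside is precision. With n test-retest pairs and normal differences, the relative standard error of the typical error is about 1/√(2(n − 1)). For n = 200 that is 1/√398 = 5.0%, for n = 100 it is 1/√198 = 7.1%, and for n = 50 it is 1/√98 = 10.1%. The 95% intervals are thus roughly ±10%, ±14% and ±20%. These assume that all 200 participants complete both visits; the number on each protocol is not stated.

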Expired gas samples will be collected into 100 - 150 L Douglas bags (Cranlea & Hans Rudolph) via a mouthpiece connected to a two-way, T shaped non-rebreathing valve (Model 2700, Hans Rudolph Inc, Kansas City, Missouri). This valve is connected to a 3-way stopcock valve (Hans Rudolph Inc, Kansas City, Missouri) through falconia tubing (Cranlea). Expired gas samples will be analysed for concentrations of oxygen and carbon dioxide through paramagnetic and infrared transducers, respectively (Mini MP 5200, Servomex Group Ltd., Crowborough, East Sussex, UK). The sensors will be calibrated to a two-point low and high calibration (Low: 99.998% Nitrogen, 0% Oxygen and carbon dioxide; High: Balance nitrogen mix, 20.06% oxygen, 8.11% carbon dioxide) using certified, known concentrations (BOC Industrial Gases, Linde AG, Munich, Germany). The sensors will be turned on for 30 minutes prior to each trial. Ambient oxygen and carbon dioxide concentrations will also be noted during collection of expired gas samples to adjust for changes in these concentrations which may have occurred due to global climate change and laboratory contamination [71]. Expired gas samples will be analysed for at least two minutes and until values are stable. Volume and temperature of expired gas samples will be measured using a dry gas meter (Harvard Apparatus) and digital thermometer (HI98509 Checktemp® 1, Hanna Instruments Ltd, Bedfordshire, UK), respectively, during gas evacuation. Ambient temperature, humidity and barometric pressure will be recorded through a weather station (Technoline WS 6730, TechnoTrade Import-Export GmbH, Berlin, Germany).

Substrate use rates will be estimated at rest and during exercise through the stoichiometric equations outlined by Jeukendrup and Wallis [72] including adjustment for the contribution of glycogen metabolism during exercise.

Anthropometric Measurements and Body Composition Analysis (DEXA Scan)

The following anthropometric measurements will be taken: a) Body mass to the nearest 0.1 kg using electronic weighing scales (BC-543 Monitor, Tanita, Tokyo, Japan); b) Body stature to the nearest 0.1 cm using a wall mounted/attached stadiometer (Holtain Ltd, UK) with participants head positioned in the Frankfort plane and after inhalation of a deep breath [73]; c) Body mass index (BMI) calculated as mass in kilograms, divided by the square of participant's stature in metres (kg/m^2); d) Fat mass index calculated as fat mass in kilograms

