Participants will then be instructed to start cycling at the required RPM (either 30 or 40) and follow the remaining respective protocol until volitional exhaustion. The stop-watch will be started when the RPM of the first stage is reached and stopped immediately upon termination of test. Expired gas samples are collected in the final minute (3-4 minute) of the first 7 stages and a final expired gas sample (between 30-60 seconds) collected when participants give the identified one minute signal to volitional exhaustion. This final sample allows estimation of $\dot{V}O_2$ peak. If a participant continues past this minute, the above process is repeated until volitional exhaustion is reached. If the final expired gas sample spans across two stages, the intensity will be increased and variance in RPM recorded to appropriately calculate peak power output. The mouthpiece is removed in between stages and provided one-minute before each collection to ensure adequate 'flushing' (excluding final collection). Expired gas samples will be analysed immediately after collection with ambient readings returning to stabilised readings between time-points before the next bag is analysed. Additionally to ensure stabilised ambient gas concentrations are recorded, the Servomex sensor will be left on after analysis of final gas sample until environmental readings are stable with any discordant values (i.e. below these final readings) adjusted for in the indirect calorimetry calculations. Heart rate (HR) via telemetry (Polar RS400 Heart Rate Monitor, Kempele, Finland) and ratings of perceived exertion (RPE; on a scale ranging from 6 = no exertion to 20 = maximal exertion [Borg, 1973]) will also be recorded during each expired gas sample. Verbal encouragement is provided throughout the test and participants are allowed ad-libitum water intake and use of fans. Participants will be asked and reminded throughout the test to keep the cadence constant and as close as possible to the desired RPM. Consistent or repetitive deviations in RPM (± 3) will be recorded to appropriately calculate power output.

Sample Size Estimation

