A sample size estimation of 200 participants was determined via two methods. Firstly, R² values (36% and 13%) from two stepwise multiple linear regression models predicting the variance of peak fat use during exercise (g/min and mg/kg Fat Free Mass/min, respectively) in 300 healthy male and female adults were used [54]. Using these R² values, 42 and 119 participants were required, respectively, to provide a 95% chance of detecting this variation in PFO with α set at 0.05. Secondly, Cohen [76] defines the above effect sizes as large and

medium, respectively. A sample size estimation chart produced by Miles and Shevlin [77] with ten predictors was consulted as a guide. Conservatively, to detect a medium effect size with a power of >95%, approximately 180-190 participants would be required. Taking into account the above, a sample of two-hundred participants was decided upon to account for rolling recruitment, loss of follow-up data due to study withdrawal, non-completers, replacement of drop-outs and any unforeseen issues in data collection.

To minimise the negative impact of loss of follow-up data to validity, participants will be provided with a detailed participant information sheet and have the experimental protocol explained verbally before the onset of the study. They will be advised to carefully consider the required time investment and effort required to complete the study. As such, we hope that exclusions based on likely withdrawals can be accounted for prior to participation. Any unforeseen change in circumstance or withdrawal of consent resulting in loss of follow-up data will be fully documented in the final trial report.

Statistical / Data Analysis

Primary Outcome Measure:	Maximal rate of whole-body fat oxidation (mg/kg FFM/min)
Secondary Outcome Measures:	Maximal rate of whole-body fat oxidation (g/min)
	FAT _{MAX} (% of maximum oxygen consumption)
	FAT _{MAX} (% of Watt max)
	FAT _{MAX} (% of Heart Rate max)
	Resting rate of whole-body fat oxidation (mg/kg FFM/min)
	Resting rate of whole-body fat oxidation (g/min)
	Resting Metabolic Rate (kcal/min)
	$\dot{V}O_{2peak}$
	Habitual Energy Intake (kcal/day)
	Habitual Macronutrient Intake (grams per day)
	Habitual Physical Activity Energy Expenditure (kcal/day)

	Menstrual Cycle (Self-reported and sex hormone concentrations in blood [Estrogen and Progesterone])
	Fasting measures of blood metabolites: Glucose, Triglycerides, Cholesterol, NEFA, glycerol

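### The rule for correcting ambient gas readings runs in one direction and names no gas; that direction suits O2 but is wrong for CO2, so calculated fat oxidation could be biased upward

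*Combined protocol and SAP*

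**What the plan says.** Three statements in the Combined protocol and SAP bear on this.

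- **Collecting and Analysis of Expired Gas Sample (Indirect Calorimetry).** "Ambient oxygen and carbon dioxide concentrations will also be noted during collection of expired gas samples to adjust for changes in these concentrations", the stated causes being those "which may have occurred due to global climate change and laboratory contamination". Both gases are therefore recorded, and the readings are meant to follow real changes in room air.
- **Incremental graded maximal cardiorespiratory cycling exercise test (FATmax), between bags.** Bags are analysed straight after collection, "with ambient readings returning to stabilised readings between time-points before the next bag is analysed".
- **Same section, after the last bag.** "Additionally to ensure stabilised ambient gas concentrations are recorded", the sensor is left running until the readings are stable, "with any discordant values (i.e. below these final readings) adjusted for in the indirect calorimetry calculations".

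The last sentence does not say which gas is meant, how far below counts as discordant, or what the adjustment is. Fat oxidation is then derived from gas exchange: "Substrate use rates will be estimated at rest and during exercise through the stoichiometric equations". The primary outcome in Statistical / Data Analysis is the peak of that rate per kilogram of fat-free mass.

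**The concern.** Expired gas is poorer in O2 and richer in CO2 than room air. If some remains in the analyser when ambient air is read, O2 comes out too low and CO2 too high. A test for values below the final reading therefore finds the O2 error and cannot find the CO2 error. For CO2, the only readings it can flag are low ones, and these may be true readings taken before room CO2 had risen.

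Fat oxidation depends on a small difference between VO2 and VCO2, so a small error in inspired CO2 becomes a noticeable error in the outcome. Overstated inspired CO2 lowers VCO2 and raises calculated fat oxidation. The protocol shapes the test to "capture peak fat use in the beginning stages", and those stages are the furthest in time from the final ambient reading.

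**Working it through.** The plan states no figure for this correction, so there is none to reproduce. The check is a sensitivity calculation.

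**Assumed inputs (not in the documents).** Ventilation VE of 15, 25 and 35 L/min; expired O2 of 16.5%, 16.4% and 16.4%; expired CO2 of 3.85%, 4.00% and 4.05%; ambient O2 20.90%; true ambient CO2 0.04% or 0.06%. Expired fractions are taken as correct. An adjusted reading is assumed to be fully replaced.

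**Formulas.**
- VI = VE × (1 − FEO2 − FECO2) / (1 − FIO2 − FICO2)
- VO2 = VI × FIO2 − VE × FEO2
- VCO2 = VE × FECO2 − VI × FICO2
- Fat (g/min) = 1.675 × (VO2 − VCO2). The plan does not print its coefficients. This one follows from tripalmitin stoichiometry, with 2.013 L O2 used and 1.416 L CO2 produced per gram: 1/(2.013 − 1.416) = 1.675.

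**Base case, VE 25 L/min, ambient CO2 0.04%.** VI = 25 × 0.796/0.7906 = 25.171. VO2 = 25.171 × 0.2090 − 4.100 = 1.161. VCO2 = 1.000 − 25.171 × 0.0004 = 0.990. Fat = 0.286 g/min.

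**Case A: the rule is applied to CO2 and a true early value is raised.**
- +0.01 percentage point: VO2 1.161, VCO2 0.987, fat 0.291 (+1.9%).
- +0.05 points: VO2 1.164, VCO2 0.977, fat 0.313 (+9.3%).
- Over the three ventilations and both ambient values: +1.7% to +2.1% per 0.01 point, and +8.3% to +10.3% per 0.05 points.

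**Case B: 1% of the expired gas remains when ambient air is read, and only O2 is corrected.**
- O2 reads 20.90 − 0.01 × (20.90 − 16.40) = 20.855%.
- CO2 reads 0.04 + 0.01 × (4.00 − 0.04) = 0.0796%.
- Neither corrected: VO2 1.149, VCO2 0.980, fat 0.283 (−1.0%). Both inspired-to-expired differences shrink by 1%, so the two errors nearly cancel.
- O2 restored to 20.90%, CO2 left at 0.0796%: VO2 1.163, VCO2 0.980, fat 0.307 (+7.4%).
- At VE 15 and 35 the corresponding results are +6.5% and +8.2%. With true ambient CO2 of 0.06%, the three ventilations give +6.3%, +7.1% and +7.9%.

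Case B follows whether the rule is meant for O2 only or for both gases, because a CO2 reading that is too high is not below anything. Case A arises only if the rule is also applied to CO2. Fat-free mass is a fixed divisor, so the percentage change at a given stage carries over to mg/kg FFM/min.

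**The case against.** The strongest reply is that the sentence is about O2. Its aim is to catch readings that have not settled, and looking for low values makes sense only for O2. The plural in the opening clause gives the purpose of the step and does not define which values are discordant. On that reading no true CO2 value is touched, and CO2 stays with the time-matched readings of the indirect calorimetry section. This removes Case A but not Case B.

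The protocol also requires ambient readings to restabilise before each bag is analysed. That safeguard covers both gases and should make discordant readings less common. It stands as a limit on frequency. The protocol nevertheless provides a correction for such readings, so it allows for some.

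A reader might go further and infer that the rule overwrites early CO2 values with the end-of-test value and so inflates the primary outcome. The documents do not support that. They do not say the rule is applied to CO2, they say only that values are adjusted for, and they give no room readings showing that CO2 rises during a test. If it is flat, or has fallen back by the final reading, no true early value is raised.

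Nor is the error shown to be largest in the early stages. Per 0.01 point it is 0.0032, 0.0053 and 0.0075 g/min at 15, 25 and 35 L/min, so it grows with ventilation even as the gap to the final reading closes. An artefactual link with fitness (Objective 2) and added day-to-day noise (Objective 3) are possible, but nothing in the documents shows either.

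**Conclusion.** The concern holds as a fault in the rule. A single downward test is wrong for CO2, and neither reading of the sentence handles CO2 correctly. In both situations examined, the resulting error in calculated fat oxidation is upward: about 2% per 0.01 percentage point if a true CO2 value is raised, and about +7% to +8% (nearer +6% at the lowest ventilation tried) if a 1% residue is corrected for O2 alone, against about −1% with no correction.

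These are sensitivities under assumed ventilation, gas fractions and residue, with full replacement of adjusted values. They are not estimates of the bias in this study, whose frequency and size the documents do not allow anyone to work out. The rule as written also leaves room for two analysts to process the same test differently.

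**What to change.** Rewrite the sentence by gas. An ambient O2 reading is discordant if it lies below the stable ambient value, and a CO2 reading if it lies above it, in each case by more than a stated tolerance. When a reading is discordant, correct both gases together, using the adjacent stable ambient readings. Otherwise keep the time-matched readings described in the indirect calorimetry section. Apply the same rule to any tests already processed.

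The cost is one sentence in the protocol and a change to the calculation spreadsheet, using readings already recorded.
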